**Protocol Version 1.13 April 4, 2020**

**1. Background and specific aims:** In the United States (U.S.), Black women are three times more likely to experience iron deficiency (ID) in pregnancy compared to women from other racial/ethnic groups, for reasons that remain largely unknown. Women who are iron deficient during pregnancy experience higher rates of maternal and infant mortality, preterm birth, low infant birth weight, and irreversible neurocognitive defects in their children. Indeed, the highest rates of adverse maternal-infant health outcomes occur in Black women, a phenomenon that may be driven by their sub-optimal iron status. Specific to Chicago, in some low income predominately Black neighborhoods (e.g. Englewood, Austin), preterm birth rates range between 18.5% and 34.8% far exceeding the national average of 9.6% and the state of Illinois at 10.3%. *Exposure to structural violence may compromise maternal iron status that contributes to adverse maternal-infant health outcomes in Black women in at-risk communities.*

Black women nationally and in Chicago are more likely to live in urban areas that are fraught with **structural violence**. Structural violence refers to the multiple ways in which social, economic, and political systems disproportionately expose particular populations to risks and vulnerabilities including poverty, crime, violence, and limited access to healthcare and healthy foods that contribute to excess morbidity and mortality. These socio-environmental exposures likely interact with biology to drive maternal-infant health disparities in Black women including maternal ID. Specifically, chronic exposure to **structural violence** can dysregulate the stress response (i.e., hypothalamic pituitary adrenal (HPA) axis) eliciting altered production of glucocorticoids (i.e., cortisol) and a propagated pro-inflammatory immune cascade. Such stress-induced changes can adversely affect the health of pregnant women and their offspring. In fact, exposure to chronic stress is associated with ID and decreased dietary iron absorption. In pregnant women, exposure to chronic stress is also associated with lower infant iron status at birth which is concerning given iron is essential to postnatal neurodevelopment. Stress-induced inflammation alters iron metabolism by promoting production of the iron-regulatory hormone hepcidin. Elevated hepcidin reduces dietary iron absorption and access to body iron stores that leads to ID. In our preliminary study, pregnant Black women exposed to **structural violence** (i.e., discrimination) had elevated hepcidin compared to those not exposed ([name], unpublished). Importantly, providing supplemental dietary iron to a stressed and iron deficient woman in pregnancy will not correct the underlying ID due to the negative effects of elevated hepcidin on dietary iron absorption. Thus, interventions that can safely and effectively mitigate the physiologic effect of stress (i.e., inflammation) have the potential to improve maternal and infant iron status that reduces suboptimal pregnancy and birth outcomes.

There is growing evidence that probiotic bacteria can reduce stress and its adverse physiologic effects. For instance, daily probiotic consumption is associated with reduced cortisol output and decreased self-reported stress in healthy volunteers. The gut, gut bacteria, and mental health are intimately linked through the gut-microbiota-brain axis, a system that mediates the molecular interactions between intestinal bacterial communities and host neurological, immunological and endocrinological processes. Therefore, the effect of probiotics on stress is likely mediated through modulation and recolonization of the gut microbiota with commensal microbes, such as lactobacilli, that promote positive effects on the HPA axis (i.e., cortisol output) and the pro-inflammatory immune response. Presumably, such effects would also normalize iron metabolism. Notably, supplementation with *Lactobacillus Plantarum* 299v (Lp299v) has been linked to reduced cortisol in stressed patients, decreased systemic inflammation, and enhanced dietary iron absorption. Probiotics are safe for use in pregnancy, thus, Lp299v may be a safe and inexpensive daily probiotic therapy to improve iron status of women burdened by exposure to chronic stress from structural violence in pregnancy. Additionally, we recognize that health-related resources for pregnant women are limited in many of the marginalized neighborhoods of Chicago. Thus, along with pilot testing a potentially innovative therapy aimed at reducing the physiologic effects of chronic stress from structural violence, we strive to build a sustainable university-community partnership to disseminate research findings and promote lifestyle and dietary approaches to mitigate the effects of chronic stress from structural violence for at-risk pregnant Black women in Chicago.

*Our specific aims are as follows:*

**Specific Aim 1:** To determine the impact of consuming daily Lp299v + standard PNVI vs. standard PNVI + placebo beginning between 15-20 weeks gestation through delivery on maternal iron status and metabolism. To fully characterize maternal iron metabolism and regulators of maternal iron metabolism we will measure several blood-based markers including hemoglobin, hematocrit, ferritin, transferrin receptor, transferrin saturation, serum iron, erythropoietin, systemic inflammation and hepcidin at baseline, 24-28 and 34 - 36 weeks gestation, and at

delivery. *Hypothesis: Women consuming Lp229v will have superior iron status at –24-28 and 34 - 36 weeks gestation and at delivery compared to control women.*

**Specific Aim 2:** To determine colonization and propagation of the gut microbial community with Lp299v from rectal swabs collected at baseline, 24-28 weeks and 34 - 36 weeks gestation in women consuming Lp299v + standard PNVI vs. standard PNVI + placebo. *Hypothesis: Women consuming LP299v will have greater colonization and propagation of Lp299v in their rectal swabs at –24-28 week and 34 - 36 weeks gestation compared to women consuming PNVI + placebo.*

**Specific Aim 3:** To explore the effect of daily oral Lp299v vs. placebo on infant iron status at delivery. Infant iron status will be measured (via cord blood at delivery) (i.e., hemoglobin, ferritin, transferrin, serum iron, and transferrin receptor). *Hypothesis: Infant of women consuming LP299v will have higher iron status at delivery.*

**Specific Aim 4:** To determine the feasibility and tolerability of daily oral Lp299v supplementation (15-20 weeks gestation-delivery). *Hypothesis: Feasibility and tolerability will be high in both treatment groups of the study for the duration of the trial.*

**Exploratory Aim 1:** There is some evidence that probiotic use can positively influence maternal health outcomes including mood. We will explore differences in the development of gestational hypertension, pre-eclampsia, and gestational diabetes using data extracted from the electronic health record (EHR). We will also examine changes to maternal stress response (i.e., serum 17-hydroxycorticosterone and hair cortisol via immunoassay) and self-reported stress, depression, anxiety, resilience, experiences of discrimination, childhood trauma, social support, post-traumatic stress, and spirituality via surveys in women consuming Lp299v + standard PNVI vs. standard PNVI + placebo.

**Exploratory Aim 2:** To build a sustainable university-community partnership to disseminate research and promote lifestyle and dietary approaches to mitigate the physiologic effects of chronic stress from structural violence for at-risk pregnant Black women in Chicago. We will conduct the Maternal Stress Reduction Project, “Happy Moms”, which entails focus groups and a demographic questionnaire to inform future programming and curriculum.

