- a. **Lp299v + standard PNVI.** Starting at 15-20 weeks gestation, women assigned to this group will consume Lp299v + standard PNVI capsules each, once daily, through delivery. Women will be asked to consume both pills with dinner along with a cold or room temperature beverage. The Lp299v supplement will be provided by NatureMade, Pharmavite. This probiotic formulation has a bacterial density of  $10^{10}$  colony forming units (CFUs) per capsule. The PNVI is from NatureMade, Pharmavite and the nutrient content is comparable to a standard prenatal plus vitamin prescribed by clinicians at UIC. The PNVI contains 27 mg of iron as ferrous fumarate. The pills will be provided in separate Pillsy containers and labeled as Vitamin and just generically as “supplement”. Women will receive 30-40 days of pills at the baseline visit and asked to start taking the pills on the 1st day of the 15th-20th gestational week. [name], Associate Professor of Clinical Obstetrics & Gynecology at UIC and Director of the Center for Women’s Health, will write the prescription for both the Lp299v and standard PNVI. The UIC Pharmacy will fill the prescription and deliver to the CRC. Women will pick up new pills at UIC every 28 days during a scheduled standard care prenatal visit or during a separate pill pick up or research data collection visit. If necessary, research staff will hand deliver supplements to the participant home if requested.
- b. **Standard PNVI + placebo.** Starting at 15-20 weeks gestation, women assigned to this group will consume standard PNVI + placebo once daily, through delivery. Taste and packing of the placebo will be identical to the Lp299v, minus the Lp299v, and will be produced by the UIC Pharmacy. Women will be asked to consume both pills with dinner along with a cold or room temperature beverage. The PNVI is from NatureMade, Pharmavite. The PNVI nutrient content is comparable to a standard prenatal plus vitamin prescribed by UIC clinicians. The PNVI contains 27 mg of iron as ferrous fumarate. The pills will be provided in separate Pillsy containers and labeled as Prenatal Vitamin Tablets and Probiotic or Placebo Capsules. Women will receive 30 days of pills at the baseline and asked to start taking the pills on the 1st day of the 15th-20th gestational week. Women will pick up new pills at UIC every 28 days and whenever possible during a scheduled standard

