**Nature Made Nutritional Products**  
[name], U.S.A.  
[name] • [www.NatureMade.com](http://www.NatureMade.com)

USP has tested and verified ingredients, potency and manufacturing process. USP sets official standards for dietary supplements. [www.uspverified.org](http://www.uspverified.org)

†This statement has not been evaluated by the Food and Drug Administration. This product is not intended to diagnose, treat, cure or prevent any disease.

**VI. Research-related visits.** Data will be collected at baseline (<20 weeks gestation), 24-28 and 34-36 weeks gestation and at delivery. Tolerability [potential adverse events (AEs) (e.g., GI symptoms)] will be assessed via phone/email/text weekly for the first 4 weeks and bi-weekly thereafter. Compliance data will be collected at pill pick-up visits (scheduled around usual care prenatal visits whenever possible) and during research visits. Women will be called or texted and emailed 2-3 days prior to each research-related visit and reminded of their appointment time, location and instructions how to prepare (e.g., fast for 2 hours, bring their pill containers). The visits will take place at the Clinical Research Center [name]. The research-related visits and data collected at each visit are described below:

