7. Adult violence exposure. This is a 29-item survey used to identify exposure to violence of the past 7 days. The survey is used to classify low- and high-violence exposure that has demonstrated good construct validity, internal consistency, test-retest reliability, and validity.
8. Social support – MOS social support survey. This survey was designed to be comprehensive in terms of recent thinking about the various dimensions of social support.
9. Healthy Pregnancy Stress Scale. This is an 18-item scale that measures pregnancy stressors women have experienced during their pregnancy.
10. Hair collection survey. This survey was developed by the research team and asks about hair care practices.
11. Short Scale Anxiety Sensitivity Index (SSASI). This is 5-item scale that measures anxiety.
12. Behavioral Inhibition System & Behavioral Activation System Scales. This is a 24-item scale that measures behavioral inhibition and activation.
13. Brief Irritability Test (BITe). This is a 5-item scale that measures irritability.
14. Generalized Anxiety Disorder 7-item (GAD-7) Scale. This is a 7-item scale that measures anxiety.
15. IDAS-II III Temper (Anger) Scale. This is a 5-item scale that measures anger.
16. Intolerance of Uncertainty Scale – Short Form. This is a 12-item scale that measures intolerance of uncertainty.
17. Pittsburgh Sleep Quality Index. This is a 24-item scale that measures sleep.

Hair collection (34-36 weeks only): If the woman agrees, a sample of hair will be collected from the crown of her head (70-100 strands) by trained research staff.

Rectal Swab (baseline, 24-28 and 34-36 weeks): If the woman agrees, using the kit provided, she will collect two rectal swabs.

Maternal health data: We will abstract from the EHR data pertaining to recent illness or infection, new medications, and change in health status (i.e., development of a pregnancy related condition like gestational diabetes).

Pill pick up and adherence monitoring (24-28 weeks and 34-36 weeks gestation):

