**IX. Rectal swabs processing and analyses.** All maternal rectal swabs will be processed at [name] 3060/3028 COMRB lab space and stored at  $-80^{\circ}\text{C}$  until analysis. Bacterial DNA will be extracted from the rectal swab using a commercial kit following standard procedures. The microbial community will be assessed via 16s rRNA analysis, whole genome shotgun sequencing, and qPCR.

**X. Placenta analysis.** Placenta will be used to assess gene expression of iron regulatory, inflammatory proteins, and tissue iron content. Placenta will be weighed, measured, and systematically biopsied and frozen at  $-80\text{C}$  for gene and protein analysis.

*i. Nucleic acid extraction: total RNA will be extracted from homogenized placental samples by the UIC DNA services lab and shipped to UCLA for the gene expression analyses.*

*ii. Gene (mRNA) expression: 8 representative biopsy samples will be taken, with the fetal and maternal membranes removed for later mRNA expression analyses (qPCR). The samples will be placed in RNA later and stored at  $-80\text{C}$  until analyses.*

**XI. Hair analysis.** Exposure to chronic stress will be assessed by measuring cortisol from a small hair sample (70-100 strands) using a commercial ELISA kit (Alpco Diagnostics, Salem, NH). Hair cortisol has been validated against 24-hour urine cortisol as a relevant biomarker of long-term cortisol exposure.

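### Aim 2 claims colonization and propagation of Lp299v, but both follow-up swabs fall inside daily dosing, so an arm difference cannot separate either from passage of swallowed organisms

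*Combined protocol and SAP*

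**What the plan says.** Specific Aim 2 (protocol section 1) is "To determine colonization and propagation of the gut microbial community with Lp299v from rectal swabs collected at baseline, 24-28 weeks", with a third collection at 34-36 weeks. Its hypothesis is directional: "Women consuming LP299v will have greater colonization and propagation of Lp299v in their rectal swabs" at both follow-up times, compared with placebo.

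Methods V.a sets the exposure: "Starting at 15-20 weeks gestation, women assigned to this group will consume Lp299v + standard PNVI capsules each, once daily, through delivery". Each capsule holds 10^10 CFU and is taken with dinner. No break in dosing is described.

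Methods VI.b gives the sampling: "Rectal Swab (baseline, 24-28 and 34-36 weeks): If the woman agrees, using the kit provided, she will collect two rectal swabs". The labor and delivery section collects maternal blood, cord blood and placenta, but no swab. The COVID-19 changes add no later swab, and no postpartum visit is described. Methods VI gives as visit preparation "instructions how to prepare (e.g., fast for 2 hours, bring their pill containers"; nothing fixes the interval between the last capsule and the swab.

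Methods IX describes DNA extraction and then states: "The microbial community will be assessed via 16s rRNA analysis, whole genome shotgun sequencing, and qPCR". Methods XIII compares microbial abundance, diversity and metabolism between groups at each time, adds within-group change, and explores the swab microbiome as a mediator of the effect of Lp299v on maternal stress and iron outcomes. No section defines colonization or propagation.

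**The concern.** Propagation ordinarily means multiplication, and colonization suggests an organism that has established itself. To support either, the data must look different when the organism is established from when it is merely passing through. Here one arm swallows Lp299v every evening and the other never does, and both follow-up samples are taken while that contrast is in force. The plan's test of Aim 2 could come out positive with no establishment or multiplication at all.

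This limit is separate from the choice of assay or statistic. The documents do not say whether the qPCR has a strain-specific target, but a perfect strain-specific qPCR would leave the same ambiguity.

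What is at stake is the conclusion drawn from a numbered aim. The background proposes that probiotics act on stress through re-establishment of commensal bacteria in the gut. A positive Aim 2, in its present wording, would be read as evidence for that mechanism.

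**Working it through.** The documents give no detection rate, effect size or power for Aim 2, so there is no stated figure to reproduce. The check is one of timing.

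**1. Swab windows against dosing.** Inputs: dosing starts at 15-20 weeks and ends at delivery (V.a); follow-up swabs are at 24-28 and 34-36 weeks (VI.b). Shortest time on dosing = window start − 20; longest = window end − 15.

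| Swab | Shortest | Longest | Off-dose by design |
|---|---|---|---|
| 24-28 weeks | 24 − 20 = 4 weeks | 28 − 15 = 13 weeks | No |
| 34-36 weeks | 34 − 20 = 14 weeks | 36 − 15 = 21 weeks | No |

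Planned off-dose follow-up swabs: 0 of 2.

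**2. What each explanation predicts.** If Lp299v establishes and multiplies, its DNA is higher in the active arm at both times. If it only passes through, its DNA is again higher in the active arm at both times, because only that arm ingests it. The planned between-arm comparison has the same expected direction under both. A viability or replication measure might discriminate, but IX and XIII plan neither.

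**3. Can passage alone give a positive test?** This is an illustration on assumed detection rates with no colonization, assumed equal arms, and Fisher's exact test at two-sided 0.05.

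| Women swabbed per arm | Detection, Lp299v vs placebo | Power |
|---|---|---|
| 20 | 80% vs 10% | 0.997 |
| 20 | 60% vs 10% | 0.91 |
| 20 | 50% vs 5% | 0.89 |
| 10 | 80% vs 10% | 0.84 |
| 10 | 60% vs 10% | 0.47 |

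Twenty per arm is the planned 40 women split equally (the allocation ratio is not stated). Ten per arm allows for swabs being optional. A positive result from passage alone is therefore easy to obtain if on-dose detection is common, and far from certain if it is not.

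**4. Could missed doses supply off-dose swabs?** Assume 20 women × 2 follow-up visits = 40 visit samples in the Lp299v arm, and independent daily misses. Expected samples after a gap of k days = 40 × (1 − adherence)^k. The plan's feasibility target is 85% adherence, and its non-compliance cut-off is 75% (VI).

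| Gap | At 85% | At 75% |
|---|---|---|
| 1 day | 40 × 0.15 = 6 | 40 × 0.25 = 10 |
| 2 days | 40 × 0.0225 = 0.9 | 40 × 0.0625 = 2.5 |
| 3 days | 40 × 0.0034 = 0.14 | 40 × 0.0156 = 0.6 |

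Misses may cluster, which would raise the counts for longer gaps, but those samples would come from women selected by non-adherence. They cannot carry a persistence claim.

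**The case against.** The strongest reply is that this is a matter of vocabulary. The documents never define colonization as persistence without re-supply. Aim 2 compares women while they are consuming the product, so it can be read as asking whether Lp299v is present in the gut community during supplementation. On that reading the sampling schedule is adequate. This stands in part: no sampling error is alleged, and no extra swab is required. It does not rescue propagation, which on its ordinary meaning of multiplication is not measured by any planned analysis.

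Four stronger conclusions might be inferred, and the documents do not support them.

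- *The swabs can show only that swallowed bacteria are recovered.* The plan also compares abundance, diversity and predicted metabolism and looks at within-group change, so wider community effects during supplementation can be studied. Shotgun data might in principle support a replication estimate, but none is planned.
- *A positive Aim 2 is nearly certain.* That depends on detection rates the documents do not give. In the illustration, power runs from 0.47 to 0.997.
- *The mediation analysis rests on a variable meaning colonized.* No such variable is defined. Stress and iron outcomes at 24-28 and 34-36 weeks are also measured on treatment, so the on-treatment microbiome is a reasonable candidate mediator at those times.
- *The share of swabs taken soon after a dose measures the error.* It describes recent exposure, not the chance of a wrong conclusion, and it rests on assumed transit time and independent misses.

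**Conclusion.** The point holds as a mismatch between claim and design. Both follow-up swabs lie inside daily dosing, no off-dose follow-up swab is scheduled, and the DNA-based work comes with no planned viability or replication analysis. An arm difference in Lp299v therefore cannot be attributed to colonization or multiplication rather than passage of recently swallowed organisms.

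This rests on the documents' own schedule and on reading propagation as multiplication. It needs none of the assumed detection rates, adherence patterns or transit times. Its size is the structural count, 0 of 2; the data give no basis for quantifying a probability of error. The swabs keep their value for showing Lp299v recovery and community differences during supplementation. In a 40-woman pilot this calls for a correction to the aim, hypothesis and conclusion, and leaves the data collection as planned.

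**What to change.** 1. Restate Aim 2, its hypothesis and its eventual conclusion as *detection and quantity of Lp299v DNA in rectal swabs during daily supplementation, compared with placebo*. Remove colonization and propagation from all three.
2. For each follow-up swab, derive time since the last capsule from the Pillsy record, which is downloaded at the same visits, and report recovery against it descriptively. This assumes the record dates each bottle opening, and an opening is not proof of ingestion. Present it as an exposure check only, with no persistence claim from swabs taken after missed doses.
3. Where Lp299v abundance enters the mediation models in XIII, state in advance that it is interpreted as on-treatment exposure, not as established colonization.

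The cost is a more modest claim, one derived variable and a sentence of interpretation. Dosing, visits, specimens and tests are unchanged, and the rewording can equally be applied when results are reported.

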## 2. Methods.

- I. **Research participants.** We will recruit and enroll 40 women early in pregnancy (< 20 weeks gestation) from the University of Illinois at Chicago (UIC) Obstetrics (OB) clinics located at the University of Illinois Hospital and Health Sciences System (UIHHSS) Outpatient Care Center, Center for Women’s Health. Women will be between the ages of 18 – 45 years old and at risk for maternal ID based on hemoglobin of 10.0 – 11.9 g/dl assessed as part of standard clinical care during the first prenatal OB visit.
- II. **Eligibility, recruitment, and informed consent:** After obtaining a waiver of consent for recruitment purposes, we will complete a pre-screen eligibility checklist of women < 20 weeks gestation who are seeking prenatal care at the UIC Obstetrics Clinics at the UIHHSS Center for Women’s Health. Potentially eligible women will be identified through clinic schedules and eligibility assessed via Cerner/EHR (only if data is available, data will not be available for new UIC patients). Women identified as potentially eligible through the EHR data or new UIC patients attending their first OB prenatal appointment will be approached in clinic. A research team member will introduce the study, assess interest, and further determine eligibility using a screening checklist. Interested and eligible women will be asked to provide contact information. As part of routine care, maternal hemoglobin will be assessed following the first OB visit. For women that express interest in the study and provide contact information, hemoglobin results will be followed up in Cerner. Women will be called regardless of their results to report on continued study eligibility. If hemoglobin is within the study defined range (10.0 – 11.9 g/dl) women will be invited to participate. Those who continue to express interest will be asked to schedule a baseline appointment at the UIC Clinical Research Center (CRC)s. Women will be consented at the baseline visit. Research personnel will explain to every eligible woman that their choice to participate will in no way affect their standard of care at UIHHS.

